### **13. Exclusion and interruption of trials:**

Regular monitoring and quality control of the study will be carried out. If the physician responsible for the study deems it necessary, the physician may during treatment take the subject out of the study. The physician may also terminate the study at any time if there is a medical justification (such as the development of allergies to medicines), a safety risk or a requirement from the authorities. The test subject may also withdraw their informed consent and withdraw from the investigation at any time, as mentioned in the above paragraph.

### **14. Information on compensation and compensation schemes:**

Patients who participate in these studies and who believe they have suffered injury can seek compensation through the patient compensation (<http://patienterstatningen.dk/>) cf. Danish law.

## **Introduction**

In the ongoing coronavirus pandemic, COVID-19, that arose in Wuhan China, there is still sparse data in the course, risk of various complications, and how patients who are hospitalized are best treated to ensure high survival and short hospitalization. Despite the rapid spread of the disease globally, there is no robust data yet to recommend any specific treatments, which is why symptomatic, organ supportive therapy, including respiratory therapy in acute pulmonary failure, is recommended. There has been reported a high incidence of bacterial super-infections in patients with COVID-19. Patients with COVID-19 also have a higher risk of mortality because of septic shock. Thus, there is an urgent need for treatment that can improve the patient's chance of the shorter hospitalization and treatment that can lower the risk of secondary infection and death.

This is a randomized, placebo-controlled, double-blinded multi-center trial evaluating the effect of azithromycin and hydroxychloroquine treatment in patients with COVID-19 during hospitalization. The aim of the study is to investigate whether the therapy can shorten hospitalization, reduce the risk of non-invasive ventilation, admittance to intensive care units and death

The patients are enrolled in the trial only after obtaining informed consent. The trial is conducted at eight centers in Denmark.

1. Section of Respiratory Medicine, Herlev-Gentofte Hospital, Copenhagen, Denmark  
Principal investigator: [name], Senior Consultant, Research [name], PhD. Co-founder of COP:TRIN ([www.coptrin.dk](http://www.coptrin.dk)).
2. Department of Respiratory Medicine, Hvidovre Hospital, and University of Copenhagen  
PI: [name] [name]. Head of the Respiratory Research Unit and the Management of Asthma during Pregnancy (MAP) program at Hvidovre Hospital.
3. University Hospital North Zealand Hospital, department of Pulmonary and Infectious diseases. PI: [name] Senior consultant, MD
4. Respiratory Medicine at the Bispebjerg Hospital, Copenhagen,  
PI: [name], Senior Consultant, Research associate professor
5. Respiratory medicine department, Zealand Hospital, Næstved and the University of Southern Denmark. PI: [name], Research Associate Professor, Senior Consultant in Respiratory Medicine
6. Respiratory medicine department, Odense University Hospital, Odense, Denmark. pi: [name], Research Associate Professor, Senior Consultant in Respiratory Medicine
7. Respiratory medicine department, Aarhus- and Aalborg University, PI: [name], Research Associate Professor, Senior Consultant in Respiratory Medicine

Patients will be randomized to one of the two treatment arms:

- i) **Intervention group:** Azithromycin day 1-3: 500 mg x 1, day 4-15: 250 mg x 1  
Hydroxychloroquine: Day 1-15: 200 mg x 2
- ii) **Control group:** The control group will always receive the standard treatment and placebo for both types of intervention medication. If part or all the intervention therapy being investigated becomes standard treatment during the study, this may also be offered to the control group.

The analyses described in this document will be performed by [name], PhD coordinating investigator, in cooperation with the sponsor and principal investigator [name], research associate professor, Respiratory Medicine Section, University of Gentofte Hospital, once the data have been entered, cleaned and released for use.

This document provides a detailed description of the statistical analyses that will be performed for the evaluation of the primary and secondary endpoints of protocolized for the ProPAC-COVID study.

The analyses described in this document are compatible with the recommendations of the CONSORT 2010 statement.

The International Conference on Harmonisation (ICH) of Good Clinical Practice (GCP)(1) and leading experts recommend that randomized clinical trials should be analyzed according to predefined outcomes and a predefined detailed statistical analysis plan (2). To prevent selective reporting of outcomes and data-driven analysis results and increase transparency this paper will in detail describe the detailed statistical analysis plan for the ProPAC-COVID trial while enrolment of patients and collection of data is still on-going and before the database is accessed for trial results.

### **Sample size**

The power to avoid type II error is 80% (1- $\beta$ ) at a two-sided 5% significance level, using a t-test for the primary outcome, and a group-sequential design allowing for one interim analysis at half target recruitment. This provides a sample size of 226 subjects. All confidence intervals reported will be 95% confidence intervals.

### **Analysis Software**

All analyses will be performed using SAS software version 9.4.

## **DATA ANALYSIS**

### **Descriptive analyses – Baseline characteristics at study enrollment (defined as day 1).**

The following baseline characteristics of the study population will be summarized separately within each randomized group:

- Age, median (IQR), y
- Male sex, n (%)
- Ethnicity (Caucasian, African (incl. Afro-American), Asian, Inuit, Unknown/other)
- Body mass index ( $\text{kg}/\text{m}^2$ , median, IQR)
- Current smoker, n (%)
- Ex-smoker, n (%)
- Nonsmoker, n (%)
- Pack-years history (median, IQR, y)
- Use of oxygen therapy, n (%)
- Use of CPAP, n (%)
- Use of noninvasive mechanical ventilation, n (%)
- Infiltrate on Chest X-ray, n (%)
- Oxygen consumption: L/min (median, IQR)
- Oxygen consumption:  $\text{FiO}_2$  (median, IQR)

### Clinical findings

- Systolic blood pressure (mm Hg)
- Diastolic blood pressure (mm Hg)
- Heart rate, beats/min
- Oxygen saturation with nasal oxygen, median, IQR
- Respiratory rate, breaths/min
- Temperature (°C)

### Biochemistry findings (daily measurements)

- Leukocyte count,  $\times 10^9$  cells/L
- Blood eosinophil count,  $\times 10^9$  cells/L
- CRP (mg/L)
- Fibrin D-dimer
- Ferritin
- Lactate Dehydrogenase (U/L)

### Arterial Blood Gas (mean $\pm$ SD) day 1 and day 4

- PCO2, mmHg
- PO2, mmHg
- HCO3
- pH

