## **5. Blood samples:**

As part of usual care, blood samples are taken daily from the time of inclusion and as long as the patient is admitted. Blood samples include haemoglobin (Hb), leukocytes + differential count, thrombocytes, C-reactive protein (CRP), Na+, K+, albumin, creatinine, urea, amylase, alkaline phosphatase, beta-2-Microglobulin, fibrinogen, glucose, TSH, D-dimer, APTT, calcium, triglycerides, ferritin, bilirubin, ALAT, INR, and lactate dehydrogenase (LDH), see Table 1. These blood samples are analysed at the hospitals.

In addition, supplemental blood tests and material obtained with nasal swabs will be performed according to the sub-study protocols. Material from this will be included in a research biobank for the trial, and after completion of the trial in another regional biobank. The trial is expected to end in February 2021, and the material will then be transferred to the regional biobank.

For the present trial, the results of blood tests are collected from the patient record.

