## Proactive Prophylaxis With Azithromycin and Chloroquine in Hospitalised Patients With COVID-19 (ProPAC-COVID)

Common (1-10%) Powerlessness, Decreased appetite. Vomiting, Taste Disorders. Decreased lymphocyte count. Decreased serum bicarbonate. Arthralgia. Headaches, Paraesthesia, Dizziness. Skin itching, rash. Visual disturbances.

Uncommon (0.1-1%) Pain. Hepatitis, Oral candidiasis. Dyspnea, Pneumonia, Oedema. Eosinophilia, Leukopenia, Neutropenia. Elevated serum bicarbonate, Hyperchloremia, Hyperglycaemia, Hyperkalaemia, Hyponatremia, Hypokalaemia, Hyponatraemia. Arthritis, Back Pain. Nervousness, Somnolence. Facial oedema, Dermatitis, Photosensitivity. Candidiasis, Infections. Metrorrhagia, Kidney Pain, Testicular Disease, Vaginitis. Hearing loss, Tinnitus.

Rare (0.01-0.1%) Cholestasis, Liver Impact. Agitation. Acute generalized exanthematous pustulosis\*, Allergic reactions\*, Angioedema\*, Hypersensitivity.

Not known Fulminant hepatitis, Hepatotoxicity, Hepatic insufficiency, Pancreatitis, Pseudomembranous colitis. Arrhythmias, Extended QT interval, Hypotension, Torsades de pointes tachycardia. Haemolytic anaemia, Thrombocytopenia. Aggravated myasthenia gravis. Aggressiveness, Anxiety, Delirium, Hallucinations, Hyperactivity, Hypesthesia, Seizures, Syncope. DRESS - drug reaction with eosinophilia and systemic symptoms, Erythema multiforme, Stevens-Johnson syndrome, Toxic epidermal necrolysis. Anaphylactic reaction. Acute renal failure, Interstitial nephritis.

\*In case of allergic reactions, including acute generalized exanthematous pustulosis and DRESS, azithromycin should be discontinued.

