### Hydroxychloroquine:

Very common (> 10%) Abdominal pain, Nausea.

Common (1-10%) Eating refusals. Diarrhoea, Vomiting. Emotional lability, Headaches. Skin itching, rash. Accommodation difficulty.

Uncommon (0.1-1%) Liver effect. Nervousness, Sensomotor disorders, Dizziness. Alopecia. Corneal oedema, Double vision, Retinopathy \*, Tinnitus.

Not known Fulminant liver failure. Bronchospasm, prolonged QT interval\*\*, Cardiomyopathy. Aplastic Anaemia, Bone Marrow Depression, Influence of the Blood Image (agranulocytosis, anaemia, leukocytopenia, thrombocytopenia). Aggravation of Porphyria, Hypoglycaemia. Myopathy. Extrapyramidal genes, Cramps, Neuropathy, Palsy, Psychosis, Suicidal behaviour. Acute generalized exanthematous pustulosis\*\*\*, Exfoliative dermatitis, Erythema multiforme, Photosensitivity, Stevens-Johnson syndrome, Toxic epidermal necrolysis. Allergic reactions (including DRESS syndrome), Angioedema. Hearing loss, Macular and retinal degeneration, Maculopathy.

\*Retinopathy:

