## Proactive Prophylaxis With Azithromycin and Chloroquine in Hospitalised Patients With COVID-19 (ProPAC-COVID)

- With pigment change requires careful dosing and careful control. When using rheumatologic doses, eye examination by an ophthalmologist is recommended before starting treatment and with follow-up to check for any eye manifestations that may arise. Annual monitoring after 5 years of treatment is recommended, however in risk patients initially annual control, see also Chloroquine derivatives (inflammatory rheumatic diseases), side effects.
- With cardiomyopathy can be fatal.
- With macular degeneration is seen and may be irreversible.
- With reversible corneal changes with oedema and blemishes can cause blurred vision or photophobia.
- With blurred vision accommodation is dose-dependent and reversible.
- In malaria treatment and prophylaxis, fewer and milder side effects occur.

\*\*Prolonged QT interval has been seen in patients with particular risk factors for it.

\*\*\*Acute generalized exanthematous pustulosis must be distinguished from psoriasis. Psoriasis exacerbation may occur. May be associated with fever and hyperleukocytosis.

An adverse reaction (AR) is defined as any adverse and undesirable reaction to a trial drug regardless of dose. An adverse event (AE) is defined as any adverse event in a patient or subject in a clinical trial following treatment with a drug, without necessarily linking this treatment to the adverse event.

Since the trial drugs are well known and have been used for many years, we will only record side effects not mentioned in the respective drug summary of the trial drug.

A severe adverse reaction or event (SAR/SAE) is defined as an event or adverse event that, regardless of dose, results in death, is life-threatening, results in hospitalization or prolongs hospitalization, results in significant or persistent disability or incapacity, or leading to a congenital anomaly or malformation.

Investigators must immediately (= within 24 hours) report serious incidents and serious adverse reactions (SAEs and SARs) to the sponsor regardless of whether they are described in the respective product summary. This allows the sponsor to assess the benefits and risks along the way in the study.

Events and adverse events recorded during the period from the patient have received the first dose of trial medication up to and including day 15.

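### Liver, kidney, glucose, potassium, haemoglobin, neutrophil and platelet results are collected daily in hospital and match listed drug harms, but the SAP plans no by-arm post-baseline analysis of them

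*SAP*

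**What the plan says.** **Collection.** Protocol section 5 states that "blood samples are taken daily from the time of inclusion and as long as the patient is admitted". The panel includes "haemoglobin (Hb), leukocytes + differential count, thrombocytes, C-reactive protein (CRP" and continues with sodium, potassium, "albumin, creatinine, urea, amylase, alkaline phosphatase, beta-2-Microglobulin, fibrinogen, glucose, TSH, D-dimer" and, further on, bilirubin, ALAT and INR. For this trial "the results of blood tests are collected from the patient record". Section 3.3.3 separately lists kidney function, liver parameters, electrolytes and the differential count among the information to be obtained.

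**Listed harms.** Protocol section 6 names, for azithromycin, "Fulminant hepatitis, Hepatotoxicity, Hepatic insufficiency", along with leukopenia, neutropenia, thrombocytopenia, haemolytic anaemia, hyperglycaemia, high and low potassium, and acute renal failure. For hydroxychloroquine it names liver effects, fulminant liver failure, bone marrow depression, anaemia and "Aggravation of Porphyria, Hypoglycaemia". It lists no kidney or potassium harm for hydroxychloroquine.

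**Recording.** Section 6 also says "we will only record side effects not mentioned in the respective drug summary of the trial drug". Serious events and reactions go to the sponsor within 24 hours whether labelled or not, and the authority receives a final report.

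**Analysis.** The SAP's list headed "Biochemistry findings (daily measurements" stands under the baseline characteristics, defined as day 1 and summarised by randomised group. It holds leukocytes, eosinophils, CRP, D-dimer, ferritin and LDH. The post-baseline organ-safety items, at the end of the secondary outcomes, are QTc above 500 ms and ventricular arrhythmias.

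**The concern.** Three parts of the plan do not connect. The protocol names toxicities that routine bloods would show, the bloods are taken and retrieved, and the SAP then does not use them to compare the arms. In many trials an adverse-event table would partly cover this. Here the rule against recording labelled side effects removes most of that cover, because these laboratory toxicities are labelled.

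At stake is the harm side of the report for a two-drug combination. If the plan is followed as written, a reader of the main paper would see cardiac safety and mortality by arm and nothing on liver, kidney, glucose, potassium, haemoglobin, neutrophils or platelets. That silence could be taken for absence of harm. The primary result is not affected.

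**Working it through.** **1. Tests, listed harms and planned analysis side by side**

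| Test group (Protocol section 5) | Harm listed for azithromycin | Harm listed for hydroxychloroquine | By-arm post-baseline analysis named in SAP |
|---|---|---|---|
| Liver: ALAT, bilirubin, INR | yes | yes | none |
| Kidney: creatinine | yes | no | none |
| Glucose | yes (high) | yes (low) | none |
| Potassium | yes (high and low) | no | none |
| Haemoglobin, neutrophils, thrombocytes | yes | yes | none |
| Leukocytes, eosinophils | yes | leukocytes only | unclear: under baseline, but headed as daily |

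ALAT, bilirubin, INR, creatinine, glucose, potassium, haemoglobin, neutrophils and thrombocytes appear nowhere in the SAP. Renal insufficiency, liver failure and haematological disease appear only as comorbid conditions at baseline.

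**2. Other routes.** The SAP's interim content is selected baseline data, the primary outcome and 30-day mortality, although Protocol section 4 describes that analysis as focused on safety. Serious events have a reporting route, but neither document specifies a table of them by arm.

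**3. Number per arm.** Protocol section 3.3.6 gives a difference of 1.5 days, SD 4, two-sided 5% and 80% power. The normal approximation is 2 × (1.96 + 0.842)² × 4² / 1.5² = 111.6, so 112 per arm, 224 in total. The t-test solution is 112.6, so 113 per arm, which reproduces the plan's 226. This serves only to fix n = 113 below.

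**4. What a laboratory comparison could show**, before adjustment for baseline and with all 113 per arm contributing:
- 95% CI half-width: 1.96 × √(2/113) = 0.26 SD
- Shift detectable with 80% power: (1.96 + 0.842) × √(2/113) = 0.37 SD

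Sampling stops at discharge, so these are best cases. The documents give no figure for how many patients would contribute. With an assumed 80 per arm they become 0.31 and 0.44 SD, and with an assumed 60 per arm 0.36 and 0.51 SD.

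**5. What event counts could show**
- Hydroxychloroquine liver effects are listed at 0.1-1%: 113 × 0.001 = 0.11 to 113 × 0.01 = 1.13 expected cases per arm.
- Zero cases in 113: one-sided 95% upper limit 1 − 0.05^(1/113) = 2.6%.
- Power to compare threshold crossings, with assumed rates and all 113 per arm having data, is Φ[(d − 1.96·SE₀)/SE₁], where d is the difference in proportions, SE₀ its pooled and SE₁ its unpooled standard error: 30% for 5% vs 10%, 71% for 5% vs 15%, 93% for 5% vs 20%.

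Continuous values carry more information than counts, but both are descriptive at this sample size.

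**The case against.** The strongest reply is that the gap is narrower than it looks.

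- **Some labelled effects may be summarised.** If the biochemistry heading is read literally, leukocytes and eosinophils get a daily summary by arm. The blood gas list gives bicarbonate on days 1 and 4, and decreased bicarbonate is a listed azithromycin effect. The SAP also mentions transforming biochemical markers for parametric analyses. This stands for those analytes. It does not reach liver, kidney, glucose, potassium, haemoglobin, neutrophils or thrombocytes.
- **Adverse-event routes are not fully closed.** Section 3.3.3 lists adverse events among the data, and the restriction in section 6 is worded for side effects. Serious cases reach the sponsor and the authority. This also stands, but no by-arm comparison follows from any of it.
- **The SAP does not forbid the analysis.** A reader might infer that its rule against further analysis after unblinding bars laboratory safety work. It does not: coded-arm analysis before unblinding remains open. The SAP confines itself to primary and secondary endpoints, and the protocol announces exploratory endpoints without naming them. The supportable statement is that nothing is planned, not that nothing can be reported.
- **A mean shift is not toxicity.** A shift of 0.37 SD in log ALAT is not hepatotoxicity and should not be set against rare event counts as if both measured the same thing. This is fair, and it is a reason to call the table descriptive.
- **Worst values are biased by length of stay.** The maximum, the minimum or any crossing becomes more likely with more samples, and the trial hypothesises that stay differs by arm. This is correct and shapes the fix.

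**Conclusion.** The point holds in a limited form. Results for liver, kidney, glucose, potassium, haemoglobin, neutrophils and thrombocytes are gathered daily during admission and correspond to listed harms, yet the SAP names no by-arm post-baseline analysis of any of them. Non-serious labelled toxicity in these tests therefore has no planned comparison, and serious cases are reported without one.

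Two stronger readings are not supported. One is that all these tests match harms of both drugs: in the protocol's lists, kidney and potassium harms belong to azithromycin only. The other is that laboratory toxicity would go unreported altogether: serious cases have a reporting route, and leukocytes, eosinophils and bicarbonate may be summarised by arm.

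The obtainable precision is at best 0.26 SD (CI half-width) and 0.37 SD (80% power), assuming all 113 per arm have a post-baseline sample. The change is worth making because the data are already collected, but it leaves the primary result, sample size and error rate untouched.

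**What to change.** Before unblinding, add to the SAP, next to the arrhythmia items, a descriptive laboratory safety table by coded arm.

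- **Main comparison.** Over a fixed early window (days 2-4), take the last available value of each analyte, on the log scale where suitable. Compare arms by ANCOVA on the day-1 value, with a 95% CI and the number of patients contributing per arm.
- **Secondary description.** Give the highest and the lowest in-hospital potassium and glucose, since harms are listed in both directions, and the worst value of the other analytes. Add n (%) crossing the limits in the protocol's exclusion criteria (glucose below 3.0 mmol/L, spontaneous INR above 1.5, eGFR below 45 ml/min/1.73 m²). These serve as reporting cut-offs only, not as rules for managing patients.
- **Exposure to sampling.** Show samples and days observed per patient by arm, and warn that the secondary description depends on length of stay.
- **Clarification.** State whether the SAP's biochemistry list is a day-1 or a daily summary.

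The cost is one SAP paragraph, one table and some extra data extraction. The comparisons are descriptive, without multiplicity control. Values after discharge remain unavailable although dosing may run to day 15, and the early window says nothing about later toxicity.

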### Other Lab findings

- QTc (F) (via electronic measurement on ECG at baseline)

### Comorbid conditions, n (%)

- Asthma
- COPD
- Bronchiectasis
- Interstitial lung disease
- Allergy
- Diabetes mellitus
- Previous myocardial infarction
- Heart failure
- Atrial fibrillation
- Chronic renal insufficiency
- Essential hypertension,
- Osteoporosis
- Peripheral vascular disease

- Cerebrovascular disease
- Hematological diseases
- Depression
- Past or present lung cancer
- Previous cancer (which is not lung cancer)
- Former DVT or pulmonary embolism
- Liver failure
- Rheumatic diseases

### **Follow-up data /missing data**

% followed for each outcome data parameter will be reported for all predefined outcomes (primary and all secondary). If exploratory outcome analyses will be planned by the study group on suggestion from the reviewers/editors, % followed /missing data will also be reported for these outcomes.

### **Adherence data:**

N + % patients in both arms who:

- Started azithromycin
- Started hydroxychloroquine
- Completed azithromycin (all days)
- Completed hydroxychloroquine (all days)
- Completed both drugs (all days)

### **Medication during hospitalization**

- Type of antibiotics (non-study drugs)
  - Ciprofloxacin, Piperacillin/tazobactam, Ceftazidime, Meropenem, Colistin,
  - Gentamycin, Amoxicillin, Amoxicillin/Clavulanic, Surlid, Dicloxacillin, Penicillin, Azithromycin or other
- Days with antibiotics - any (Median days on any type)
- Days with corticosteroids (Median days)

For continuous variables, means and standard deviations will be presented, when normally distributed, otherwise as medians and interquartile ranges (IQR). For categorical variables, the number and percentage of participants within each category will be presented. For each variable, the percent of missing values will be reported. For categorical values, chi-square, Fisher's exact test. For time-to-event variables Cox regression and log-rank test will be used and for the latter, a corresponding Kaplan-Meier plot will be presented.

